Our initial retrospective study suggests that QbMRI has adequate sensitivity to detect acute ciTBIs in children. The study was presented at 2 national conferences in the spring of 2016 (Society for Academic Emergency Medicine and Pediatric Academic Society) with a manuscript currently under review.¹² This preliminary study included all pediatric trauma patients presenting to OHSU from 2/2010 through 12/2013 who had both a head CT and QbMRI. The current standard of care in the pediatric ICU at OHSU is for patients admitted with an acute head injury to undergo routine QbMRI follow up to assess status of the injury rather than a repeat head CT. Our study team collected clinical data on these patients that included clinical interventions and then de-identified all head CT and QbMRI images for this cohort. The images were then independently reviewed by 2 neuroradiology fellows at OHSU (Please refer to **Figure 1**). The sensitivity of QbMRI to detect any radiographic injury was 85% (95% CI: 73, 93), but increased when evaluating clinically important TBIs to 100% (95% CI: 89, 100). The largest limitation of this study was the variable and often long time interval between acquisition of the head CT and QbMRI. The average length of time between the initial head CT and QbMRI was 27.5 hours with only 41% receiving both imaging tests within 12 hours of each other. Also, our preliminary data was collected by retrospective review. As such, it is very promising that our initial study had high sensitivity, but further prospective pilot data with a shorter interval between the index and reference test is needed to assess the discrepancy between the two types of lesions (radiographic vs clinically important) and feasibility of obtaining qbMRI in the setting of acute pediatric head trauma. While our study did not miss any clinically important TBIs, on further review of radiographic “missed lesions”, the study pediatric neurosurgeon noted signs of a healing bleed. This may suggest that they were “missed” because they were healed rather than present and not seen. All patients that did not have a lesion identified on QbMRI did not require significant clinical interventions and only underwent periods of observation in the hospital. However, this raises the need for a prospective trial to obtain QbMRI imaging within the same time frame sequentially after the initial head CT. The current proposed pilot study will provide further data to guide a larger, future multicenter study.

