Specific Aims:

There are 3 specific aims for this study during the grant period:

- D. Develop a feasible protocol for obtaining QbMRI for children presenting to the emergency department with acute head injury.
- E. Prospectively test the diagnostic accuracy of qbMRI for detection of acute pediatric TBI in the emergency care setting compared to head CT as the reference standard.
- F. Evaluate the feasibility of obtaining QbMRI in the emergency department to assess acute pediatric brain injury, including need for sedative medications, time to imaging, and provider satisfaction.

Outcomes:

1. Primary Outcome: Test characteristics of QbMRI to detect acute pediatric TBIs, including sensitivity, specificity, positive/negative predictive value and positive/negative likelihood ratios.
2. Secondary Outcomes: Develop formal protocol to be employed for further clinical evaluation and trials on QbMRI in pediatric head trauma; assess feasibility of obtaining QbMRI in the emergency department to include need for anxiolysis/sedation, time to imaging and provider satisfaction.

Hypothesis:

We hypothesize there is no significant difference of sensitivity and specificity of QbMRI for detection of clinically important traumatic brain injuries as compared to non-contrast head CT in patients less than 15 years presenting with head trauma. We hypothesize that it will be feasible to obtain QbMRI in the emergency department without increased use of anxiolysis/sedation or prolonged time to obtain imaging

4. Study Design:

Overview: The study will be a prospective cohort study of diagnostic accuracy comparing QbMRI (index test) to non-contrast head CT (reference test). Children being evaluated for acute TBI with head CT will then undergo QbMRI in the emergency department. Only subjects who the attending physician has decided to obtain neuroimaging in will be enrolled; therefore subjects will not undergo imaging just for the study. The results of the QbMRI will not be used for clinical care. All images will be de-identified prior to review by the neuroradiologist including patient name, hospital and date.

5. Study Population:

Inclusion criteria:

1. The patient presents to the pediatric emergency department or trauma system at OHSU or is a trauma system transfer patient to OHSU
2. Age 0-14 years.
3. Being evaluated for a traumatic head injury and attending physician decides to obtain a head CT.

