4. Clinically stable for additional testing: provider deems it safe to obtain a QbMRI in the ED without deep sedation

Exclusion criteria:

1. Subject is from outside hospital and head CT was performed greater than 6 hours prior
2. Subject is from outside hospital and initial head CT is not in our imaging system for review
3. History of intracranial surgery
4. History of metallic implants making MRI contraindicated
5. Decompressive surgery prior to QbMRI

Study Procedure:

The Clinical Research Investigative Study Program (CRISP) volunteers who are on duty in the emergency department between the hours of 7 am and 11 pm will screen all ED patients for eligibility including pediatric trauma system entries. They will identify possible subjects based on suggestive chief complaints (e.g. head injury, trauma, fall, etc.) and approach the attending physician about whether the subject is being evaluated for possible acute head injury and will be receiving neuroimaging. If so, they will approach the family and review the consent forms with them for participation. After subjects are found to be eligible (see above inclusion/exclusion criteria) and consented, the physician will order the study QbMRI to be done after the head CT. QbMRIs are available to our pediatric ED at all hours as it is standard of care for other indications as described previously. Subjects will only be enrolled in the study if the attending physician feels they warrant neuroimaging with a head CT. After undergoing a QbMRI, their clinical care will be the same whether they are in the study or not. A copy of the images will then be de-identified and placed in separate review folders in the electronic radiology system so they cannot be linked (ie. One folder for head CTs and one folder for QbMRIs) for review by an attending neuroradiologist. Clinical data including length of stay, procedures performed and disposition will be collected directly from EPIC.

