QbMRIs will be obtained in the MRI scanner at OHSU available to the ED. The protocol will consist of a QbMRI protocol modified to include a blood-sensitive T2* sequence. No intravenous contrast will be administered. It is not anticipated that any sedation or anti-anxiety drugs will be administered to patients. However, this is reflected in the consent that a small portion of children will need for any type of neuroimaging. For this reason, parents may decline participation. No deep sedation drugs will be administered as that will fall under the definition of clinically unstable in the exclusion criteria. The protocol consists of:

- Coronal single-shot T2 weighted ultrafast spin echo
- Sagittal single-shot T2 weighted ultrafast spin echo
- Axial T2* weighted gradient recall echo

After a subject undergoes their imaging in the MRI suite, their further disposition will be selected by the attending physician as what they feel is necessary including admission to the hospital, observation or discharge.

Traumatic Brain Injury on neuroimaging will be defined as previously published¹ to include:

- Intracranial hemorrhage or contusion
- Cerebral edema
- Traumatic infarction
- Diffuse axonal injury
- Shearing injury
- Midline shift of intracranial contents or signs of brain herniation
- Skull fracture depressed by at least the width of the table of the skull
- Pneumocephalus

Number of Subjects:

A total of 100 subjects will be enrolled in this pilot study. To generate an approximate study timeframe and potential patient sample, EPIC was accessed to identify all patients less than 19 years of age who were seen in the OHSU emergency department in 2015 and had a “CT Head WO contrast (CPT code 70450)” performed while in the ED. This resulted 363 patients. As a large referral center, OHSU receives many transfers from outside hospitals. In our retrospective data of trauma system activations, the majority were transfer patients with head injuries. These numbers would not be included in the 363 most likely as their neuroimaging was done at an outside hospital. A review of the trauma registry at OHSU for the year of 2015 and patient less than 19 years of age resulted 221 patients who had head and neck injuries. There is most likely overlap between these 2 data points as some trauma registry patients were not transfers and underwent head CT in our department. However, we would conservatively expect that 400 patients may be eligible for this study during a 12 month period.

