
To assess the adequacy of this proposed pilot sample, we calculated the number of positive head CTs obtained in our department. Our rate of positive findings were better than the previous study mentioned rate of 2.5% positive head CTs of all ordered. At OHSU 10% of CTs in patients less than 19 years of age were positive for an acute intracranial injury. This was generated by applying the above search criteria in EPIC and associated an intracranial injury final diagnosis code including epidural hematoma, subdural hematoma, subarachnoid hemorrhage, intracranial bleed, skull fracture and cerebral contusion. This is a very conservative estimate as the majority of transfer patients through the trauma system will have positive neuroimaging as the reason for transfer and further pediatric subspecialty care. With these numbers we would expect to enroll the 100 patients within 1 year and have at least 10-20% with a positive acute TBI when taking into account the positive imaging rate in the OHSU emergency department and transfer patients with positive imaging.

Vulnerable Populations

This study, by design, is focused on pediatric patients. It may include other vulnerable populations such as pregnant women and minorities, though they are not the focus of the study

and are not included in screening criteria. No pregnant women will be given an MRI knowingly. Prisoners will not be included in this study.

Setting

The Doernbecher Children's Hospital emergency department

Consent Process

All parents will be consented on presentation to the emergency department by a member of the study team including the CRISP team. Please find attached consent form. All children ages 7-14 will be asked to signed the assent form as well.

We are requesting a consent/HIPAA waiver for a select group of patients. Any patient who is excluded from the study after initial screening for any reason other than the LAR refusing to be included will be reviewed by the principal investigator. If the clinical team, without any input from the research team, has obtained the same imaging test this study is evaluating, QuickBrain MRI, the study team will use the imaging and data as in the rest of the protocol under a waiver. It is not possible to obtain consent due to the short time window of being in the ED. Due to the acute nature of the injuries they do not have follow up in the ED either to allow consent.

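### No CT-to-QbMRI interval limit applies to children who enter by the waiver or re-contact route, and the plan's only time rule does not say what its 6 hours are measured to.

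*Combined protocol and SAP*

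**What the plan says.** **Reason for the study.** Preliminary Data says of the retrospective cohort: "The largest limitation of this study was the variable and often long time interval between acquisition of the head CT and QbMRI". It gives a mean gap of 27.5 hours, with 41% of children having both scans within 12 hours. It raises the possibility that lesions not seen on QbMRI had healed, and asks for prospective data with a shorter gap. It also says where late scans come from: usual practice in the hospital's pediatric ICU is for "patients admitted with an acute head injury to undergo routine QbMRI follow up to assess status of the injury".

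**Time rule.** Section 5, exclusion 1, reads: "Subject is from outside hospital and head CT was performed greater than 6 hours prior". No other limit in hours is set on the gap.

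**Consented children.** Study Design says: "Children being evaluated for acute TBI with head CT will then undergo QbMRI in the emergency department". Study Procedure fixes the order of the tests: "the physician will order the study QbMRI to be done after the head CT". It also places imaging before disposition: "After a subject undergoes their imaging in the MRI suite, their further disposition will be selected by the attending physician".

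**Other routes.** Consent Process adds a waiver: "Any patient who is excluded from the study after initial screening for any reason other than the LAR refusing to be included will be reviewed". If the clinical team has already obtained a QbMRI, then "the study team will use the imaging and data as in the rest of the protocol under a waiver". A separate paragraph allows one telephone call to families who refused but whose child had a clinical QbMRI, to ask for consent to use it.

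**Analysis.** Data Analysis plans sensitivity, specificity and predictive values with 95% confidence intervals. It has no restriction, stratification or sensitivity analysis by interval. Time to imaging is listed as a feasibility outcome and is not defined as the CT-to-QbMRI gap.

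**The concern.** The study exists largely to shorten the gap between reference and index test, so the rule that controls the gap should cover every pair in the accuracy table. It does not. For transfers, the word *prior* could refer to arrival, screening, consent or the QbMRI. Under any of the first three, the CT-to-QbMRI gap has no stated cap. For the waiver and re-contact routes there is no rule at all.

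These routes are likely to supply CT-positive children, who alone determine sensitivity. Number of Subjects expects most trauma-system transfers to have positive imaging, and ICU follow-up scans are of children admitted with a head injury. A lesion that has healed by the time of a late QbMRI counts as a false negative. The table would then mix test error with lesion evolution, which is the ambiguity Preliminary Data says this study should resolve.

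**Working it through.** **1. The plan's own figures.** Preliminary Data reports sensitivity of 85% (95% CI 73 to 93) for any radiographic injury and 100% (89 to 100) for clinically important TBI. Counts are not given. Exact (Clopper-Pearson) intervals that round to the first result arise from 46/54, 50/59 or 51/60, and those that round to the second from 31/31 to 33/33. The figures are internally consistent but cannot be reproduced uniquely. The share of the cohort not scanned within 12 hours is 100 − 41 = 59%.

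**2. Conditions by route.**

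| Route | Hour limit | QbMRI in ED | Before disposition |
|---|---|---|---|
| Consented, in-house CT | none | yes | yes |
| Consented, outside CT | 6 h, end point not stated | yes | yes |
| Waiver | none stated | not stated | not stated |
| Re-contact after refusal | none stated | not stated | not stated |

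The waiver reviews children excluded for any reason except refusal. Exclusion 1 is one such reason, so on the wording a child excluded for a CT older than 6 hours can return through the waiver if a clinical QbMRI exists.

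**3. Effect of one resolved lesion.** Number of Subjects gives 100 children and at least 10 to 20% positive: 100 × 0.10 = 10 and 100 × 0.20 = 20. One such child counted as a miss changes sensitivity by 1/n: 1/10 = 10 points, 1/20 = 5 points. The number of misses below is an assumption; the intervals are exact.

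| CT-positive | 0 misses | 1 miss | 2 misses |
|---|---|---|---|
| 10 | 100% (69, 100) | 90% (56, 100) | 80% (44, 97) |
| 20 | 100% (83, 100) | 95% (75, 100) | 90% (68, 99) |

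**4. Cost of an analysis window.** With no misses the exact lower limit is 0.025^(1/n): 69.2% at n = 10, 78.2% at n = 15 and 83.2% at n = 20. If one positive child leaves the table, it moves from 83.2% to 0.025^(1/19) = 82.4%, or from 69.2% to 0.025^(1/9) = 66.4%. If 5 of 20 leave, it falls to 78.2%. How many would leave is not known.

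**The case against.** **In-house children.** A reader might infer that consented in-house children can repeat the 27.5-hour problem. The documents do not support that. Their QbMRI is done in the ED, follows the CT, is available at all hours and precedes disposition, whereas the retrospective cohort drew on scans after admission. What remains for them is an unwritten cap.

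**The waiver may be narrower than its wording.** Its justification refers to the short time a family spends in the ED, which suggests scans from the ED visit. It requires the same test as the study's, which Study Procedure defines with an added T2* sequence, and the documents do not say that ICU follow-up scans include one (Figure 1 does show T2* within a QbMRI). The phrase "the study team will use the imaging and data as in the rest of the protocol under a waiver" might also be read to import the eligibility criteria. All this makes entry of ICU scans a possible reading, not a stated plan. But the ED remark explains why consent is impracticable and sets no condition on the scan. The imported criteria cannot all apply either, because the route exists for children who were excluded.

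**A computed bias.** A reader might take 85% as the sensitivity of late pairs and mix it with a higher value for prompt pairs. The 85% is the whole-cohort figure, and 41% of that cohort was scanned within 12 hours. If prompt pairs had 100% and positives were spread evenly (both assumed), late pairs would have 1 − 0.15/0.59 = 74.6%. No source gives the late share in the new study, so no bias figure can be defended.

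**Healing and precision.** Healing is offered only as a possible explanation. The stated hypothesis concerns clinically important TBI, where the long-interval cohort already showed 100%. With 10 to 20 positives the interval is wide whatever the timing. These points stand, and they limit the concern mainly to radiographic TBI, which the primary outcome includes.

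**Conclusion.** The concern holds for the undefined end point of the 6-hour rule and for the waiver and re-contact routes. Followed as written, these rules allow the long-interval pairs that the study was designed to avoid to enter its primary analysis, and the analysis has nothing that would separate them.

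The overall size is unknown, because the expected number of children by route is not given. The only figure that follows from the documents is 5 to 10 points of sensitivity for each CT-positive child whose lesion resolves before a late QbMRI. It rests on the 10 to 20 positives that the plan gives as a minimum, with smaller steps if there are more. The downward direction rests on the plan's own suggestion of healing, which is not established.

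**What to change.** 1. State that the interval runs from CT acquisition to QbMRI acquisition, and take both times from the imaging system for every analysed child.
2. Reconcile the waiver and re-contact paragraphs in Consent Process with exclusion 1, and say whether a child excluded under the 6-hour rule may return by the waiver.
3. Apply one maximum interval, for which the plan's 6 hours can serve, as an analysis window for the primary 2×2 table across all routes. This is a rule for the analysis: it need not remove currently eligible transfers from enrolment and changes no child's care.
4. Report pairs outside the window separately, give the distribution of the interval, and add a sensitivity analysis with all pairs.

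The cost is an amended criterion, a few lines in Data Analysis and two recorded times. Some late pairs, including some CT-positive transfers, would leave the primary table and widen its confidence interval. The widening is small if one or two leave and more noticeable if several do, as the working shows. The all-pairs analysis keeps their information in the report.

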For patients who are excluded after the parent/LAR refuses the study, all charts will be reviewed. If the patient underwent the same imaging test this study is evaluating, QuickBrain MRI, by the clinical without any input from the research team, the patient family will be contacted by the study Principal Investigator as participation is generally declined in the trauma bay due to family stress. Unless at time of consent, study team noted reason for declining participation would be such that they would not be amenable to re-contact. The principal investigator will only discuss the study once with parents/LAR via phone number in EHR and detail that their child underwent the same imaging test we are studying. At that time, the principal investigator will ask for consent to include the patient in the study as nothing is needed in addition or further follow up. A telephone script has been uploaded to further detail this consent process.

Data Analysis:

All data will be entered into a RedCap database maintained on the OHSU network server requiring a username and password. Clinical data will consist of descriptive statistics. The primary outcome of whether a lesion was seen on QbMRI will be presented as sensitivity, specificity, negative predictive value and positive predictive value with 95% confidence intervals. The secondary outcome of whether patients need anxiolysis will be compared between head CT and QbMRI with an independent t-test. The QbMRI protocol will be described with language to describe the imaging.

Clearance of perivascular waist in the brain is critical for recovery after traumatic brain injury. Some of these clearance happens through a network of perivascular spaces surrounding the brain

vessels called the glymphatic system. When the glymphatic system becomes dysfunctional, enlarged perivascular spaces (ePVS) can be seen on MRI. The third outcome of this study is to evaluate the presence of ePVS in patients with concussion receiving an MRI during their emergency department evaluation. We hypothesize that changes in perivascular spaces happen over time, and therefore ePVS should not be present in these early studies.

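### Need for anxiolysis at CT and at QbMRI is a paired yes/no outcome with CT done first, but the plan uses an independent t-test and has no rule for a CT dose still active at QbMRI

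*Combined protocol and SAP*

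**What the plan says.** The combined protocol and SAP fixes the sequence in two places. The Study Design overview states: "Children being evaluated for acute TBI with head CT will then undergo QbMRI in the emergency department". Study Procedure says that "the physician will order the study QbMRI to be done after the head CT". There is no counterbalancing of order.

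Transferred children are eligible. The exclusion list removes a child only if "Subject is from outside hospital and head CT was performed greater than 6 hours prior", or if the outside CT is not in the local imaging system. Number of Subjects notes that among retrospective trauma activations "the majority were transfer patients with head injuries". Study Procedure takes clinical data from the local electronic record and names no source for drugs given before an outside CT.

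The Hypothesis section expects QbMRI to be feasible "without increased use of anxiolysis/sedation or prolonged time to obtain imaging". Data Analysis gives one method for this: "whether patients need anxiolysis will be compared between head CT and QbMRI with an independent t-test". It gives no analysis of time to imaging, although time is part of the third aim and a secondary outcome. No section says when the clock starts, or to which scan a dose is attributed.

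Consent Process also admits children whose QbMRI was obtained clinically, under a waiver or after re-contact. The order of scans is not stated for them.

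**The concern.** There are three separate problems.

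- **Method.** Need for anxiolysis is yes or no, and the same child contributes a CT value and a QbMRI value. An independent t-test treats these as two unrelated groups of continuous measurements.
- **Attribution.** A dose given for CT may still be active at QbMRI. The plan does not say whether that child counts as needing a drug at QbMRI. The answer to the hypothesis can depend on a coding choice made after the data are seen.
- **Place of CT.** For transfers, drugs given for the CT may not be in the local record. If these children enter the comparison, drug use at CT may be understated.

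Time has a related difficulty. Measured from arrival, QbMRI is later than CT in every child scanned in the stated order, however well the scanner performs.

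The feasibility hypothesis is at stake. The Background section says the pilot is to guide a larger multicentre study, so these estimates will be carried forward.

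**Working it through.** **Plan's own figure.** The sample of 100 rests on accrual and the positive-CT rate. No margin, power or sample size is stated for anxiolysis or time, so there is nothing to reproduce.

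**Inputs from the documents.** N = 100. About 4% needed anxiolysis or sedation in both groups of the cited shunt study (Background). In-house head CTs in 2015: 363. Trauma-registry head and neck injuries: 221. Expected eligible per year: 400. The two 2015 counts cover ages under 19, not 0-14.

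**Step 1: share of CTs done elsewhere (f).** Not stated, so two rough figures:
- (400 − 363)/400 = 37/400 = 9%
- 221/(363 + 221) = 221/584 = 38%, assuming no overlap and that every registry case was a transfer

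These are illustrations, not strict bounds.

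**Step 2: what the independent test does.** Two possible results in 100 children:
- *The same 4 children medicated at both scans.* The variance of each column is 3.84/99 = 0.0388. The independent standard error is √(2 × 0.0388/100) = 0.0279, giving a 95% interval of about ±5.5 points around zero. The paired data show no child changing status; the exact two-sided 95% upper limit for 0/100 is 3.6% in each direction.
- *4 at CT, 0 at QbMRI.* Independent t = 0.04/√(0.0388/100) = 0.04/0.0197 = 2.03, p = 0.044. The exact McNemar test on 4 discordant pairs gives p = 2 × 0.5⁴ = 0.125. Here the gap comes from sparse counts rather than from pairing, but it shows that the t-test is unsafe at these rates.

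**Step 3: bias in anxiolysis.** Assume equal true need p = 4% at both scans. Let m be the share of outside doses not captured, q the share of children needing a drug at QbMRI who were already dosed for CT, and c the share of those still covered. The documents give none of these three.
- Recorded CT rate = p(1 − fm)
- New-dose rate at QbMRI = p(1 − qc)
- Full carry-over, all outside doses captured (q = c = 1, m = 0): 0% − 4% = −4.0 points
- No carry-over, no outside dose captured (c = 0, m = 1, f = 38%): 4% − 2.5% = +1.5 points

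Carry-over alone is 0 to 4 points, and the combined range is −4.0 to +1.5. At an assumed p = 10% it is −10.0 to +3.8.

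**Step 4: what two measures can show.** Among in-house pairs, let b be the number of children medicated for CT with no new drug for QbMRI, and d the number medicated for QbMRI only. The new-drug difference is (d − b)/n; the any-drug difference is d/n. If only carry-over is at work, the true difference lies between them, and the gap is b/n. With b = 4, d = 0 and n = 100, that is −4 to 0 points.

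**Step 5: time from arrival.** Let g be the delay to QbMRI (from CT if in-house, from arrival if transferred) and t the time from outside CT to arrival. Mean difference = (1 − f)g + f(t + g) = g + ft. Assume g = 30-120 minutes and t = 60-360 minutes.
- f = 9%: 36 to 153 minutes
- f = 38%: 53 to 256 minutes

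None of this reflects scanner performance.

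**Step 6: would a null result be reassuring?** Treating the scans as independent groups of 100, power for 4% versus 10% is 38%; 80% power needs 283 per group. A finding of no difference would not expose the bias.

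**The case against.** The strongest case on the other side is that the plan is underspecified rather than wrong, and that little turns on it. Much of this stands.

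- A reader might infer that the plan will score a covered child as medicated for CT and not for QbMRI, giving 4% versus 0%. No such rule exists; the child could be coded either way.
- A reader might infer that the comparison is biased in favour of QbMRI. The direction is not known, because uncaptured outside doses push the other way.
- A reader might infer that CT always comes first and is often done elsewhere. The order is stated only for the consented pathway. The transfer majority refers to retrospective trauma activations, and the share expected in this study is not given.
- A reader might infer that the plan makes an invalid time comparison. Data Analysis contains none, and an arrival clock is never adopted. For time, the fault is a missing definition.
- Two obvious repairs would fail. Counting every child medicated for CT as medicated at both scans, as the sole endpoint, means QbMRI can never look better than CT. An order-to-first-image clock can still contain the wait for CT.
- Materiality is modest. This is a secondary outcome in a pilot, Study Procedure anticipates no sedative or anti-anxiety drugs, and the 4% comes from a different population.

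What does not fall is the core. The independent t-test is written into the plan, the data are paired and binary, and dose attribution is undefined. That the order cannot be changed is no answer, because the analysis and the definitions can be.

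**Conclusion.** The concern holds in a limited form, centred on the anxiolysis comparison. The planned test does not fit a paired binary outcome, and the plan cannot tell carry-over from absence of need. Carry-over alone is worth 0 to 4 points at an assumed 4% rate. With uncaptured outside doses the range is −4.0 to +1.5 points, under assumed values of q, c and m and a transfer share of up to 38%. In absolute terms this is at most four children in 100, but it is as large as the whole expected rate.

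For time, the conclusion is narrower: a definition and an analysis are missing, and an arrival clock would make QbMRI later by design. The documents do not support saying that either half of the feasibility hypothesis will be answered wrongly. The change is worth making before analysis; it does not affect the primary accuracy outcome.

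**What to change.** In Data Analysis:

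1. Replace the independent t-test with a paired binary comparison (McNemar or exact) and a paired confidence interval for the difference, in children whose CT was done at OHSU.
2. Report two separate measures for QbMRI: a new drug given for QbMRI, and any drug given for CT or QbMRI in the same visit. Show children medicated for CT and given no new drug as their own category. Apply the paired test to the first measure. The second can differ from CT in one direction only, so give it as a proportion with an exact interval.
3. For children with an outside CT, describe drug use at QbMRI without a CT comparison.
4. For the time hypothesis, do not compare arrival-based times. Compare time in scanner within child, and ready-to-start time if it is recorded. Report the CT-to-QbMRI interval separately.
5. For clinically obtained QbMRIs, record which scan came first.
6. State that order cannot be fully separated from modality, since effects such as familiarity or fatigue remain.

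**Cost.** No change in imaging or care. Transfers leave the two CT-versus-QbMRI comparisons. The time of each dose, the scan it was given for, and scan start and end times must be extracted. The protocol lists length of stay, procedures and disposition as clinical data but not these items, so their availability should be checked first.
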